5.0 Populations for Analyses

The following analysis sets will be used in the summary and analysis of study data:

- **Enrolled population:** All subjects who sign informed consent.
- **Full Analysis Set (FAS):** All subjects who were randomized to receive assigned treatment. Following the intent-to-treat (ITT) principle, subjects will be analyzed according

to the treatment group assigned at randomization. The FAS will be the primary efficacy analysis population.

- **Per Protocol Set (PPS):** A subset of the FAS who are compliant with study treatment and who do not have any relevant protocol deviations that may impact the coprimary efficacy endpoint assessments. The PPS will be analyzed according to the treatment assigned at randomization. The PPS will be a supportive efficacy analysis population and only the coprimary endpoints will be analyzed using this set.
- **As-treated population:** All randomized subjects who take at least one dose of study treatment. Subjects will be analyzed according to treatment received. The As-treated population will be used for safety analyses.

5.1 Relevant Protocol Deviations

Relevant protocol deviations are deviations that can have an impact on the primary efficacy endpoints. The impact of relevant protocol deviations on the primary efficacy results will be assessed by excluding subjects from the FAS to define the PPS in supportive analyses of the primary efficacy endpoints. Relevant protocol deviations to be considered regarding exclusion of subjects from the FAS will include the following:

- Randomized but did not take any study treatment
- No postbaseline PASI or sPGA
- Baseline BSA involvement < 10%
- Baseline PASI score < 12
- Baseline sPGA < 3
- Did not have plaque psoriasis at baseline
- Poor compliance to study medication within the first 16 weeks of treatment, <75% compliant with study treatment
- Failure to adhere to prohibited concomitant medication restrictions as described below:
 - Investigational drug or placebo taken outside of the study any time between Day 1 and the Week 16 assessment
 - Phototherapy within 4 weeks prior to the Week 16 assessment
 - Biologic medications (eg, adalimumab, etanercept, infliximab, ustekinumab) any time between Day 1 and the Week 16 assessment
 - Oral psoriasis medications any time between Day 1 and the Week 16 assessment
 - Oral corticosteroids (unless for the treatment of an adverse event) within 4 weeks prior to the Week 16 assessment
 - Topical medications/treatments that could affect psoriasis evaluations within 2 weeks prior to the Week 16 assessment
 - Medicated shampoos within 2 weeks prior to the Week 16 assessment
- Subject received treatment that was different than intended treatment at any visit prior to Week 16.

Sponsor: Bristol-Myers Squibb
Protocol no: IM011065

All subjects with relevant protocol deviations will be identified prior to Week 16 database lock and unblinding of treatment assignment for the analysis of data through Week 16 with the exception of subjects where actual treatment received is different than randomized treatment which will be determined after treatment unblinding. Relevant protocol deviations will be summarized by treatment group and deviation category for the FAS population.

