- e) Any major illness/condition or evidence of an unstable clinical condition (eg, renal, hepatic, hematologic, gastrointestinal, endocrine, pulmonary, psychiatric, neurologic, immunologic, or local active infection/infectious illness) that, in the investigator's judgment or after consultation with the Medical Monitor, will substantially increase the risk to the subject if he or she participates in the study
- f) Unstable cardiovascular disease, defined as a recent clinical cardiovascular event (eg, unstable angina, myocardial infarction, stroke, rapid atrial fibrillation) in the last 3 months

prior to screening, or a cardiac hospitalization (e.g. revascularization procedure, pacemaker implantation) within 3 months prior to screening

g) Has uncontrolled arterial hypertension characterized by a systolic blood pressure (BP) >160 mm Hg or diastolic BP >100 mm Hg

Note: Determined by 2 consecutive elevated readings. If an initial BP reading exceeds this limit, the BP may be repeated once after the subject has rested sitting for \geq 10 minutes. If the repeat value is less than the criterion limits, the second value may be accepted

h) Class III or IV congestive heart failure by New York Heart Association Criteria

i) Has cancer or history of cancer (solid organ or hematologic including myelodysplastic syndrome) or lymphoproliferative disease within the previous 5 years (other than resected cutaneous basal cell or squamous cell carcinoma, or carcinoma of cervix in situ that has been treated with no evidence of recurrence)

j) Any significant/uncontrolled neuropsychiatric illness as clinically judged by the investigator during screening or at Day 1

OR

Any lifetime history of suicidal ideation, suicidal behavior, or suicidal attempts by medical history or by electronic Columbia-Suicide Severity Rating Scale (eC-SSRS) documentation, or by answering “yes” to Question 4 or 5 which indicates a suicidal ideation severity level of 4 or 5 on the eC-SSRS at Screening or at Day 1, or is clinically deemed to have a suicide risk by the investigator

k) Prior exposure to investigational product (ie, BMS-986165)

l) If the subject has received biologics previously, the following exclusion criteria for washout will apply:

- i) Antibodies to IL-12, IL-17 or IL-23 (eg, ustekinumab, secukinumab, tildrakizumab, ixekizumab, or guselkumab) within 6 months of Day 1
- ii) TNF inhibitor(s) (e.g. etanercept, adalimumab, infliximab, certolizumab) within 2 months of Day 1

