9.6 Other Analyses

9.6.1 Demographics and Baseline Data

Demographics and baseline data will be summarized by treatment for each applicable analysis population. Categorical data will be summarized as frequency counts and percentages. Continuous data will be summarized using n, mean, standard deviation, median, minimum, and maximum unless otherwise specified.

9.6.2 *Prior and Concomitant Medications*

[figure not shown]
Prior and concomitant medications, categorized by medication group and subgroup according to the World Health Organization (WHO) Drug Dictionary, will be summarized by treatment for the As-treated population. Medications with an end date prior to the first dose of study drug will be considered prior medications.

9.6.3 *Relevant Protocol Deviations*

Relevant protocol deviations are deviations that can have an impact on the primary efficacy endpoints. The impact of relevant protocol deviations on the primary efficacy results will be assessed by excluding subjects from the FAS to define the PPS in supportive analyses of the primary efficacy endpoints. Relevant protocol deviations to be considered regarding exclusion of subjects from the FAS will include the following:

- Subject was randomized but did not take any study treatment
- Subject failed to meet any study inclusion criteria but was randomized to receive study treatment
- Subject met a study exclusion criterion which may have an impact on the coprimary efficacy endpoints but was randomized to receive study treatment
- Subject was noncompliant with study treatment within the first 16 weeks of treatment; defined as <80% compliant with study treatment
- Subject took prohibited concomitant medication prior to Week 16
- Subject received treatment different than assigned treatment at any visit prior to Week 16

All subjects with relevant protocol deviations will be identified prior to the Week 16 database lock. Relevant protocol deviations will be summarized by treatment group and deviation category for the FAS population.

9.7 *Interim Analyses*

No interim analysis is currently planned.

9.8 *Analysis and Reporting*

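### The SAP's per-protocol list no longer removes subjects who took a long-acting agent shortly before Day 1 in breach of its washout, although it removes the same kind of drug taken from Day 1

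*SAP*

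**What the plan says.** **Protocol 9.6.3** lists among the relevant deviations: "Subject met a study exclusion criterion which may have an impact on the coprimary efficacy endpoints but was randomized to receive study treatment".

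**Protocol 5.2** sets washouts before Day 1. For IL-12/17/23 antibodies (4l(i)) the text ends "secukinumab, tildrakizumab, ixekizumab, or guselkumab) within 6 months of Day 1". Rituximab (4l(iv)), leflunomide (4n) and experimental antibody or biologic therapy (4t) also carry 6 months. Other windows are shorter: 3 months for integrin, B-cell and T-cell agents (4l(iii)), 2 months for TNF inhibitors (4l(ii)), 4 weeks for systemic non-biologics (4m), phototherapy (4q) and botanicals (4u), and 2 weeks for topicals (4r) and medicated shampoos (4s).

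**SAP 5.0** defines the PPS as compliant subjects "who do not have any relevant protocol deviations that may impact the coprimary efficacy endpoint assessments".

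**SAP 5.1** then gives its own list. Its baseline items are BSA, PASI and sPGA below the entry thresholds, and "Did not have plaque psoriasis at baseline". Its medication items include "Biologic medications (eg, adalimumab, etanercept, infliximab, ustekinumab) any time between Day 1 and the Week 16 assessment" and "Oral psoriasis medications any time between Day 1 and the Week 16 assessment". Outside investigational drugs have the same Day 1 to Week 16 span. Phototherapy and oral corticosteroids count only in the last 4 weeks before Week 16, and topicals and shampoos only in the last 2.

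**SAP 2.5** discloses that the list of relevant deviations was updated. It gives no reason and does not mention washouts.

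**The concern.** Dropping the exclusion-criterion item leaves no SAP 5.1 item that catches exposure which ended before Day 1. For an agent with a 6-month washout, the protocol itself treats that exposure as relevant for longer than the 16 weeks to the coprimary assessment. A subject who entered in breach of such a washout can therefore be scored at Week 16 while still inside the window, and yet sit in a set that SAP 5.0 describes as free of deviations that may affect the coprimary endpoints.

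The list is also inconsistent with itself. A biologic on Day 1 removes the subject; the same biologic a day earlier does not.

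At stake is the purpose of the PPS. SAP 5.1 says it is there to assess the impact of relevant deviations on the primary results, and it is the only analysis under SAP 6.1.1.3 (Supportive Analysis), since SAP 2.5 removes the logistic regression. It cannot assess a class of deviation that it does not list.

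**Working it through.** The documents give no expected number of washout breaches and no planned PPS size, so there is no figure to reproduce. The check is a comparison of windows, followed by a note on scale.

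**Step 1: time from Day 1 to the coprimary assessment.** SAP 8.5 sets the Week 16 target at Day 113. 113 − 1 = 112 days after Day 1.

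**Step 2: is a dose on the day before Day 1 still inside its washout window at Week 16?** That dose is 112 + 1 = 113 days old at the target day. Months are converted as 365/12 ≈ 30.4 days.

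| Exclusion criterion | Window | Days | Inside at Week 16? | SAP 5.1 rule for use from Day 1 |
|---|---|---|---|---|
| 4l(i) IL-12/17/23 antibodies; 4l(iv) rituximab | 6 months | about 182 | Yes | Removed at any time (biologic) |
| 4n leflunomide | 6 months | about 182 | Yes | Removed at any time if classed as an oral psoriasis drug; not named |
| 4t experimental antibody/biologic | 6 months | about 182 | Yes | Removed at any time (outside investigational drug) |
| 4l(iii) integrin, B-cell, T-cell agents | 3 months | about 91 | No | Removed at any time (biologic) |
| 4l(ii) TNF inhibitors | 2 months | about 61 | No | Removed at any time (biologic) |
| 4m systemic non-biologics | 4 weeks | 28 | No | Oral psoriasis drugs at any time; oral corticosteroids in last 4 weeks only |
| 4q phototherapy | 4 weeks | 28 | No | Last 4 weeks only |
| 4r, 4s topicals, shampoos | 2 weeks | 14 | No | Last 2 weeks only |
| 4u botanicals | 4 weeks | 28 | No | Not listed |

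**Step 3: how far before Day 1 the gap reaches for the 6-month agents.** 182 − 112 = 70 days, or 10 weeks. The SAP 8.5 window for Week 16 opens at Day 100 and falls back to Day 127 if the dispensing date is missing. The reach is then 182 − 99 = 83 days to 182 − 126 = 56 days, or about 12 to 8 weeks.

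**Step 4: scale only.** About 219 subjects at 2:1 gives 146 active and 73 placebo. One subject is 100/146 = 0.7 points of the active arm and 100/73 = 1.4 points of the placebo arm. Assume the Phase 2 Week 12 PASI 75 placebo rate of 6.7% (0.067 × 73 ≈ 5 responders; 5/73 = 6.8%) and 1 to 3 placebo breaches, with everyone otherwise in the PPS. The number of breaches is my assumption; the documents give none.

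- If those removed were responders: 4/72 = 5.6% with one removed, 2/70 = 2.9% with three.
- If those removed were non-responders: 5/72 = 6.9% with one removed, 5/70 = 7.1% with three.

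The placebo rate can therefore move either way, by a few points at most on these inputs.

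**The case against.** **The list follows a coherent rule.** For phototherapy, oral corticosteroids, topicals and shampoos, SAP 5.1 applies the protocol's washout lengths to the Week 16 assessment and ignores earlier use. A reader might infer that every washout in 4l to 4u should be restored. The documents do not support that. The 2- and 4-week windows lapse long before Week 16, and a topical bullet would remove someone treated 10 days before Day 1 while keeping someone treated at Week 8. This part stands and narrows the point. The rule does not explain biologics, oral psoriasis drugs or outside investigational drugs, which the SAP removes at any time from Day 1.

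**The change is disclosed and the list is open.** SAP 2.5 reports the update, and both documents introduce the list as deviations to be considered. The protocol item also needs a judgement on impact, so it does not remove every washout breach automatically. All true. But SAP 2.5 gives a reason for dropping logistic regression and none here. If unlisted cases can be added by judgement, the set is not fully pre-specified.

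**The bias is not established.** A reader might infer that carry-over raises placebo response and pulls the PPS difference towards zero. That does not follow in general. PASI 75 is measured from the Day 1 baseline. A drug already working lowers that baseline, and as it wears off, response becomes harder to reach. The retained baseline thresholds (BSA, PASI, sPGA) also screen out subjects still well controlled at entry. This stands: no direction should be claimed.

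**Breaches should be rare.** Eligibility must be confirmed before randomization, and the protocol allows no waivers. This also stands, and is a reason to expect a small effect.

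**Conclusion.** The point holds for long-acting agents. SAP 5.1 drops the protocol's exclusion-criterion item without explanation. As a result the PPS keeps subjects who took an IL-12/17/23 antibody, rituximab, leflunomide or an experimental antibody/biologic within about 10 weeks before Day 1, although the protocol's own window still covers that exposure at Week 16. For biologics and investigational agents this also conflicts with the SAP's removal of any use from Day 1. For leflunomide that second argument depends on its being classed as an oral psoriasis drug.

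The consequence is limited to the supportive PPS estimates of the two coprimary endpoints. The FAS analysis, the testing hierarchy and the superiority conclusion are untouched. It would go too far to say that the PPS is unusable, or to attach a percentage bias to it, because the documents give neither a breach rate nor a response rate for such subjects. The conclusion rests on reading the washout length as the protocol's own measure of how long prior exposure matters. It takes no view on whether those lengths are right. This is a cheap improvement to a supportive analysis.

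**What to change.** Add one bullet to SAP 5.1: *Breach of a pre-Day-1 washout in protocol 5.2 for biologics (4l), leflunomide (4n) or experimental antibody/biologic therapy (4t).* Include 4l as a whole, because SAP 5.1 already treats all biologics alike from Day 1. Oral psoriasis medications under 4m may be added on the same ground.

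Do not add 4q, 4r, 4s or 4u. The SAP keeps comparable early on-study use of phototherapy, topicals and shampoos, and does not list botanicals.

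Identify these subjects blinded before the Week 16 lock, with the other deviations. Prior systemic and biologic treatment is already collected at screening (Protocol Table 1) and summarised under SAP 6.3.3.1, and the timing is needed for eligibility in any case. If the sponsor prefers to keep these subjects, SAP 2.5 should say why.

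The cost is one bullet, a blinded check of prior-medication dates, and a slightly smaller PPS.

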- Guidance and information for final disposition of unused study treatment are provided in [APPENDIX 2](#).

6.5.1 *Retained Samples for Bioavailability/Bioequivalence*

Not applicable.

6.6 *Treatment Compliance*

Study treatment compliance will be periodically monitored using standard drug accountability procedures (comparing the number of tablets returned to number dispensed, considering the expected regimen and any reported missed doses). Drug accountability will be reviewed by the investigative site staff at each visit to confirm treatment compliance. Site staff will discuss any discrepancies with the subject and remind the subject of the importance of compliance with the assigned regimen. A real-time monitoring platform may be used.

6.7 *Concomitant Therapy*

6.7.1 *Prohibited and/or Restricted Treatments*

Prohibited and/or restricted medications in the study are described below. Medications taken within 4 weeks prior to study drug administration must be recorded on the CRF.

- 1) Exposure to any investigational drug or placebo outside of the current study
- 2) Use of any medications/therapy that would aggravate psoriasis. These include agents such as lithium, antimalarials (quinacrine, chloroquine, and hydroxychloroquine), propranolol, indomethacin, and quinidine unless it is considered necessary for the subject's welfare and/or treatment of an AE/SAE
- 3) Use of opioid analgesics unless it is considered necessary for the subject's welfare and / or treatment of an AE/SAE
- 4) Phototherapy; use of tanning booths or therapeutic sunbathing
- 5) Any use of biologic medications (eg, adalimumab, etanercept, infliximab, ustekinumab)
- 6) Any use of oral psoriasis medications (eg, methotrexate, cyclosporine, retinoids, fumaric acid derivatives) for any indication
- 7) Any use of oral or injectable corticosteroids (prednisone, methylprednisolone, etc.), unless it is considered necessary for the subject's welfare and/or treatment of an AE/SAE
- 8) Note: otic, ophthalmic, nasal, or inhaled corticosteroids within recommended doses and with no systemic effects are permitted.
- 9) Any topical medications/treatments, which are used for any indication, that could affect psoriasis evaluation (including, but not limited to, high potency corticosteroids [WHO Classes I-V], >3% salicylic acid, urea, alpha- or beta-hydroxyl acids, anthralin, calcipotriene,

vitamin D derivatives, retinoids, tazarotene, methoxsalen, trimethylpsoralens, pimecrolimus, and tacrolimus)

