Exception: The following topical treatments may be initiated only at Week 24 per investigator's discretion in subjects who have [REDACTED] (see [Section 4.1.4](#))

- High potency corticosteroids (WHO Classes I-V), >3% salicylic acid, urea, alpha- or beta-hydroxyl acids, anthralin, calcipotriene, vitamin D derivatives, retinoids, tazarotene

Note: Low potency topical steroids (WHO Class VI and VII) are permitted on the palms, soles, face, and intertriginous areas but should not be used within 24 hours prior to any study visit. Bland emollients (defined as emollients without urea or alpha- or beta-hydroxy acids or other ingredients which are pharmacologically active) are allowed on all body regions but should not be used within 24 hours prior to any study visit.

10) Any medicated shampoos that contain corticosteroids, coal tar, >3% salicylic acid, or vitamin D3 analogues

Exception: The above shampoos may be initiated only at Week 24 per investigator's discretion in subjects who have [REDACTED] (see [Section 4.1.4](#))

11) Live vaccination

12) Any botanical preparation (eg, herbal supplements or traditional Chinese medicines derived from plants, minerals, or animals) intended to treat psoriasis or other immunological diseases.

No concomitant medications (prescription, over-the-counter or herbal) are to be administered during the study unless prescribed for treatment of specific clinical events. Any concomitant therapies must be recorded on the CRF.

The investigator should contact and confirm agreement with the Medical Monitor prior to the administration of any concomitant medications.

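### SAP 5.1's per-protocol list of prohibited medication omits injectable corticosteroids and does not name botanical or traditional Chinese medicines, both of which the protocol prohibits

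*SAP*

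**What the plan says.** **Protocol.** Section 6.7.1 lists the treatments prohibited or restricted on study. Item 7 is "Any use of oral or injectable corticosteroids (prednisone, methylprednisolone, etc".), with an exception where use is needed for the subject's welfare or to treat an AE or SAE. Item 12, listed separately, is "Any botanical preparation (eg, herbal supplements or traditional Chinese medicines derived from plants, minerals, or animals) intended to treat psoriasis" or other immunological diseases. Section 9.6.3 then defines one medication-related reason for leaving the PPS, with no limit by class: "Subject took prohibited concomitant medication prior to Week 16".

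**SAP.** Section 5.1 words the reason as "Failure to adhere to prohibited concomitant medication restrictions as described below" and gives seven sub-items: outside investigational drug or placebo, phototherapy, biologics, oral psoriasis medications, oral corticosteroids, topicals and medicated shampoos. The corticosteroid sub-item is "Oral corticosteroids (unless for the treatment of an adverse event) within 4 weeks prior to the Week 16 assessment". No sub-item names injectable corticosteroids or botanicals.

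Section 2.5 declares that the deviation list was updated, without saying which classes were left out or why. It also declares that prohibited medication no longer triggers imputation, and section 6.1.1.1 accordingly limits non-responder imputation (NRI) to discontinuation and missing Week 16 data. Section 6.1.1.3 applies the same imputation to the PPS.

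**The concern.** SAP 5.1 presents the PPS as the way to assess how relevant deviations affect the coprimary results. That works only if subjects given another effective psoriasis therapy are taken out.

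The protocol regarded both classes as able to affect psoriasis. It bans them on study and requires a 4-week washout before Day 1: exclusion 4m covers oral or injectable corticosteroids, and exclusion 4u covers botanicals. The trial runs in mainland China, Taiwan and South Korea, and the protocol names traditional Chinese medicine in both its exclusion and its prohibited lists.

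The other SAP change adds weight. Under Protocol 9.4.1.1, a subject who started prohibited psoriasis therapy in the first 16 weeks counted as a non-responder. Under the SAP that subject counts as observed. The sensitivity analyses in SAP 6.1.1.2 (LOCF, LOCF with NRI, tipping point, multiple imputation) address only discontinuation and missing data. In the public text, PPS exclusion is therefore the only coprimary analysis that still deals with prohibited medication, and a class missing from the list is dealt with nowhere.

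**Working it through.** **Step 1: compare the lists.** The plan states no figure to reproduce, so the check is item by item.

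| Protocol 6.7.1 item | SAP 5.1 | Result |
|---|---|---|
| 1, outside investigational drug or placebo | Day 1 to Week 16 | kept |
| 4, phototherapy | last 4 weeks | kept, shorter window |
| 5, biologics | Day 1 to Week 16 | kept |
| 6, oral psoriasis drugs | Day 1 to Week 16 | kept |
| 7, oral or injectable corticosteroids | oral only, last 4 weeks | injectable route absent |
| 9, topicals | last 2 weeks | kept, shorter window |
| 10, medicated shampoos | last 2 weeks | kept, shorter window |
| 12, botanicals | none | not named |

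Items 2, 3 and 11 (psoriasis-aggravating drugs, opioids, live vaccines) are also absent, but they are not psoriasis treatments and do not bear on this point.

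**Step 2: could another SAP item catch the two classes?**
- Injectable corticosteroids: no. No sub-item covers the route.
- Oral botanicals: possibly, under "Oral psoriasis medications any time between Day 1 and the Week 16 assessment". The protocol's parallel item is "Any use of oral psoriasis medications (eg, methotrexate, cyclosporine, retinoids, fumaric acid derivatives) for any indication". Its examples are conventional drugs, and botanicals have an item of their own.
- Topical botanicals: possibly, as topicals, but only in the last 2 weeks.

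**Step 3: illustrative size.** Inputs:
- About 219 subjects at 2:1 (Protocol 4.2), so 146 active and 73 placebo.
- Phase 2 PASI 75 rates of 68.9% for 3 mg BID, which the protocol expects 6 mg QD to match, and 6.7% for placebo (Protocol 2.1).
- Responders: 0.689 × 146 = 100.6, about 101; 0.067 × 73 = 4.9, about 5.
- Simplification: the whole randomized arm is taken as the PPS.

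Exclusion removes a subject from numerator and denominator. For *k* users who are all responders, among *r* responders in *n* subjects, the rate moves by r/n − (r − k)/(n − k).

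One responder excluded:
- Active: 101/146 − 100/145 = 69.18% − 68.97% = 0.2 points.
- Placebo: 5/73 − 4/72 = 6.85% − 5.56% = 1.3 points.

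Assumed 5% use, every user a responder (0.05 × 146 = 7.3, about 7; 0.05 × 73 = 3.65, about 4):
- Active: 101/146 − 94/139 = 69.18% − 67.63% = 1.6 points.
- Placebo, users among the 5 responders: 5/73 − 1/69 = 6.85% − 1.45% = 5.4 points.
- Placebo, users in addition to the 5: 9/73 − 5/69 = 12.33% − 7.25% = 5.1 points.

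**Step 4: direction.** Retained responders on placebo shrink the treatment difference; on active they inflate it. The documents do not say which arm would have more use.

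**The case against.** - **Botanicals are largely covered.** The ban reaches only products meant to treat psoriasis or other immunological disease, and an oral herbal taken for psoriasis is on plain reading an oral psoriasis medication. The conventional-drug examples are in the protocol item, not the SAP's. This stands in part: a reader might infer that the SAP lets all traditional Chinese medicine through, and the text does not support that. But coverage rests on a reading the SAP does not state, and topical products are reached only in the last 2 weeks.
- **Not every steroid injection is a deviation.** This stands. Use for the subject's welfare or for an AE or SAE is permitted and would not trigger Protocol 9.6.3. The gap is injection outside that exception.
- **The change was declared and looks deliberate.** SAP 2.5 says the list was updated, and shorter windows for other classes suggest a focus on effects at Week 16. So this is not a hidden contradiction. The declaration still gives no reason for omitting these classes. SAP 5.1's general lead-in could be read as open-ended, but the wording that introduces the medication sub-list closes it.
- **Little depends on it.** This stands. The PPS is supportive and covers only the coprimary endpoints; trial success and the testing hierarchy use the FAS. The Phase 2 contrast was 68.9 − 6.7 = 62.2 points, so shifts of this size would be unlikely to change the PPS conclusion.
- **A shift of about 5 points in either arm.** A reader might infer this by dividing users by arm size (7/146 = 4.8%). That treats users as reclassified to non-response. Under exclusion the active shift is about 1.6 points; about 5 applies to placebo only.

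**Conclusion.** The omission is confirmed from the text and needs no assumption. Injectable corticosteroids outside the protocol's exception are a clear gap; botanicals are an ambiguity. Users of an unlisted class stay in the PPS coprimary analysis at their observed response.

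The size is unknown, because the documents give no rate of use. The figures of about 0.2 and 1.3 points per responder, and about 1.6 and 5 points at 5% use, rest on the Phase 2 rates. The 5% figures also assume that rate of use and that every user responds, so they lie towards the upper end for that rate. The direction of bias depends on the arm. A reader might infer that the primary result is compromised by this list; it is not, because the FAS analysis does not use it. The point is worth correcting because the PPS is the remaining check on prohibited medication and the correction is cheap.

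**What to change.** In SAP 5.1:

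1. Widen the corticosteroid item to oral or injectable, keeping its present adverse-event exception and 4-week window.
2. Add an item for botanical, herbal or traditional Chinese medicines intended to treat psoriasis or other immunological diseases, running from Day 1 to the Week 16 assessment. A 4-week look-back borrowed from exclusion 4u would not do: it could loosen the any-time rule that may already catch oral products, and it would not match Protocol 9.6.3.
3. Identify both classes from the coded concomitant medications by blinded review before the Week 16 lock.

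The SAP exception covers adverse events only, whereas the protocol's also covers subject welfare. The blinded review should record welfare use so that permitted treatment can be told apart from a deviation; the same applies to the existing oral item.

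The cost is two list lines and one search of coded data. Concomitant therapies are already recorded on the CRF (Protocol 6.7.1) and coded to the WHO drug dictionary (SAP 6.3.3), so no new data are needed. The PPS may lose a few subjects.
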